### **2.8.3 Laboratory data**

Laboratory values will be summarized by treatment group, including changes from baseline at each time point. Frequency table of results for categorical laboratory parameters will be presented by visit and time point.

Shift tables using the low, normal, or high classification (except for eGFR and HbA1c) will be used to compare baseline to the worst on-treatment value by treatment group. All data collected after first dose of double-blind treatment, from scheduled, unscheduled and premature discontinuation visits will be used.

The following ranges will be used for eGFR and HbA1c

- For eGFR, the categories will be Severe =  $<30$  mL/min/1.73m^2; Moderate =  $\geq 30$  to  $<60$  mL/min/1.73m^2; Mild =  $\geq 60$  to  $<90$  mL/min/1.73m^2; and Normal =  $\geq 90$  mL/min/1.73m^2.
- For HbA1c, the categories will be  $<5.7\%$ ,  $\geq 5.7\%$  to  $<6.5\%$ , and  $\geq 6.5\%$ .

The shift table dealing with the fasting glucose parameter will require the lab sample to be taken while fasting. Samples taken while the participant was not fasting will not be analyzed.

For selected laboratory tests, the number and percentage of patients meeting the clinically notable criteria at any time, considering all data collected after first dose of double-blind treatment, from scheduled, unscheduled and premature discontinuation visits, will be summarized by laboratory parameter and treatment group. Notable criteria are defined in [Appendix 5.3](#). Clinically notable criteria and notable liver criteria will be considered to be met when both of the following occur:

- Post-baseline values meet the thresholds listed in [Appendix 5.3](#)
- Baseline values or any prior post-baseline values do not meet the thresholds listed in [Appendix 5.3](#)

Furthermore, the number and percentage of participants meeting notable criteria in liver function test (LFT) will be summarized by treatment group considering on-treatment data from scheduled, unscheduled and premature discontinuation visits. LFT criteria are defined in [Appendix 5.3](#).

All laboratory data will be listed by treatment group, participant, and visit/time and if normal ranges are available abnormalities will be flagged.

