### Shifts from Baseline in Glucose Control Category

Shifts from baseline in glucose control category will be summarized by treatment group in two different ways. The change from baseline to the worst-on-treatment and the last-on-treatment laboratory values (up to min (last visit, last dose +180 day)) will be used to classify the on-treatment glucose control category. Medical history will not be taken into account for this analysis.

Shift Category*	Baseline Category**	Post-baseline Category***
Normal to Normal (no change)	Fasting glucose <100 mg/dL AND HbA1c <5.7%	Fasting glucose <100 mg/dL on two consecutive occasions AND HbA1c <5.7%
Normal to Impaired	Fasting glucose <100 mg/dL AND HbA1c <5.7%	Fasting glucose $\geq$ 100 and <126 mg/dL on two consecutive occasions OR HbA1c $\geq$ 5.7 and <6.5%
Normal to Diabetes	Fasting glucose <100 mg/dL AND HbA1c <5.7%	Fasting glucose $\geq$ 126 mg/dL on two consecutive occasions OR HbA1c $\geq$ 6.5%
Impaired to Normal	Fasting glucose $\geq$ 100 and <126 mg/dL OR HbA1c $\geq$ 5.7 and <6.5%	Fasting glucose <100 mg/dL on two consecutive occasions AND HbA1c <5.7%
Impaired to Impaired (no change)	Fasting glucose $\geq$ 100 and <126 mg/dL OR HbA1c $\geq$ 5.7 and <6.5%	Fasting glucose $\geq$ 100 and <126 mg/dL on two consecutive occasions OR HbA1c $\geq$ 5.7 and <6.5%
Impaired to Diabetes	Fasting glucose $\geq$ 100 and <126 mg/dL OR HbA1c $\geq$ 5.7 and <6.5%	Fasting glucose $\geq$ 126 mg/dL on two consecutive occasions OR HbA1c $\geq$ 6.5%
Diabetes to Normal	Fasting glucose $\geq$ 126 mg/dL OR HbA1c $\geq$ 6.5%	Fasting glucose <100 mg/dL on two consecutive occasions AND HbA1c <5.7%

Diabetes to Impaired	Fasting glucose $\geq 126$ mg/dL OR HbA1c $\geq 6.5\%$	Fasting glucose $\geq 100$ and $<126$ mg/dL on two consecutive occasions OR HbA1c $\geq 5.7$ and $<6.5\%$
Diabetes to Diabetes (no change)	Fasting glucose $\geq 126$ mg/dL OR HbA1c $\geq 6.5\%$	Fasting glucose $\geq 126$ mg/dL two consecutive occasions OR HbA1c $\geq 6.5\%$

\*No change (Normal to Normal, Impaired to Impaired, and Diabetes to Diabetes), worsened (Normal to Impaired, Normal to Diabetes, and Impaired to Diabetes), and Improved (Impaired to Normal, Diabetes to Impaired, and Diabetes to Normal) categories will also be summarized.

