\*\* Baseline of fasting glucose is defined as average of Screening and Day 1 assessment. If one fasting glucose value is missing (Screening or Day 1), the baseline will be based on the available data. For HbA1c, Day 1 assessment will be considered as baseline.

\*\*\*For post-baseline categories, if the post-baseline two consecutive fasting glucose measurements fall in separate categories, or if only one post-baseline fasting glucose measurement is available, then the post-baseline glucose control category will be defined based on the HbA1c measurement only. If HbA1c value is missing and two consecutive fasting glucose measurements fall in separate categories, the lower category will be used to determine the post-baseline category.

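### Glucose shift table: two consecutive glucose readings at or above 100 mg/dL, one Impaired and one Diabetes, are classed as Normal when HbA1c is available and below 5.7%

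*SAP*

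**What the plan says.** SAP 2.8.4, under Shifts from Baseline in Glucose Control Category, sets three post-baseline categories:

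- Normal: "Fasting glucose <100 mg/dL on two consecutive occasions AND HbA1c <5.7"%.
- Impaired: two consecutive glucose values from 100 to below 126 mg/dL, or HbA1c from 5.7% to below 6.5%.
- Diabetes: two consecutive glucose values of at least 126 mg/dL, or HbA1c of at least 6.5%.

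The three-asterisk footnote covers cases in which the glucose values do not agree. It applies "if the post-baseline two consecutive fasting glucose measurements fall in separate categories", and also when only one value exists; "then the post-baseline glucose control category will be defined based on the HbA1c measurement only". When HbA1c is missing and the pair is discordant, "the lower category will be used to determine the post-baseline category".

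The one-asterisk footnote adds a summary of No change, Worsened and Improved. The table is produced for both the worst and the last on-treatment values.

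**The concern.** The three categories form an ordered scale, so raising a glucose reading while HbA1c stays fixed should never improve the category. For one type of pair it does. If one reading is in the Impaired range and the other in the Diabetes range, the footnote sets both aside and an HbA1c below 5.7% makes the participant Normal. Yet both readings show glucose of at least 100 mg/dL, which the table excludes from Normal.

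The direction matters because this is a safety table. For these pairs the category always moves towards normal. From an Impaired baseline the participant counts as Improved, and from a Normal baseline as No change.

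**Working it through.** No stated figure is to be reproduced here. The check applies the table and the footnote as written.

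**Inputs.** Glucose cuts of 100 and 126 mg/dL and HbA1c cuts of 5.7% and 6.5%, all from SAP 2.8.4. The example glucose readings are illustrative. So are the HbA1c values: one from each band (5.5%, 6.0%, 6.7%), plus missing.

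**Step 1: apply the rules.**

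| Glucose pair (mg/dL) | HbA1c | Table rows met | Result with footnote |
|---|---|---|---|
| 135/120 | 5.5% | none | **Normal** |
| 135/120 | 6.0% | Impaired | Impaired |
| 135/120 | 6.7% | Diabetes | Diabetes |
| 135/120 | missing | none | **Impaired** |
| 105/105 | 5.5% | Impaired | **Impaired** |
| 105/105 | missing | Impaired | Impaired |
| 135/95 | 5.5% | none | Normal |
| 105/95 | 5.5% | none | Normal |

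At HbA1c 5.5%, each reading in 135/120 exceeds each reading in 105/105, yet the first pair gets the better category. The order of the two readings makes no difference.

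**Step 2: move across the cut.** With HbA1c below 5.7%, 125/125 is Impaired, 126/125 is Normal and 126/126 is Diabetes. One extra mg/dL on one reading improves the category. One extra mg/dL on the other then worsens it by two.

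**Step 3: find the extent.** Three glucose bands for each of two readings and four HbA1c states give 3 × 3 × 4 = 36 combinations. Only two are classed below both of their glucose categories: Impaired/Diabetes, in either order, with HbA1c below 5.7%. In 135/95 and 105/95 the lower reading is itself Normal, so those results are not below both.

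**Step 4: follow it into the summary.** Take baseline glucose 110 mg/dL and HbA1c 5.6%. The glucose value makes the baseline Impaired. Post-baseline readings of 135/120 with HbA1c still 5.6% give Normal, so the participant is Improved. From a Normal baseline the same readings give No change.

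**Step 5: test the correction.** For a discordant pair, use

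category = worse of (lower glucose category, HbA1c category), or the lower glucose category alone if HbA1c is missing.

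Then 135/120 gives Impaired at 5.5%, Impaired at 6.0%, Diabetes at 6.7% and Impaired when missing. At 5.5% it now matches 105/105. Pairs 135/95 and 105/95 at 5.5% stay Normal. In Step 4 the Impaired-baseline participant becomes No change and the Normal-baseline participant becomes Worsened.

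**The case against.** The best defence is that the footnote is a deliberate confirmation rule. A single high value is not confirmed, so the plan turns to HbA1c, and HbA1c below 5.7% is Normal on the SAP's own HbA1c scale. A discordant pair with such an HbA1c meets no row of the table, so the footnote fills a gap. This is a fair reason not to call 135/120 Diabetes, and the correction does not. It is no reason to discard what both readings agree on, namely glucose of at least 100 mg/dL. When HbA1c is missing, the footnote itself keeps that information.

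Four stronger readings are tempting, and the documents do not support them.

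- *HbA1c alone always decides a discordant pair.* It does not when HbA1c is missing, and the reversal needs an HbA1c below 5.7%.
- *The two footnote sentences contradict each other.* They cover different cases (HbA1c present, HbA1c missing). The defect is the order of the results they give.
- *The rule hides deterioration in an adverse event of special interest.* New onset or worsening of diabetes is identified by event search criteria (SAP 2.8.1.1 and Diabetes TEAE in 2.8.4). The new-onset analysis has its own four components and does not use this footnote; its glucose component would not count 135/120 either. Worst and last fasting glucose are summarised separately, and laboratory data are listed. The readings stay visible.
- *A large share of participants is affected.* If true fasting glucose is 115 to 125 mg/dL and within-person SD is 8 to 12 (assumed, with independent normal readings), 2 × P(≥126) × P(100 to <126) gives 15% to 49% for an isolated pair. That describes only people near the cut and is not conditioned on HbA1c below 5.7%. It also looks at one pair. If worst means the worst category over all consecutive pairs, which the SAP does not say, one concordant pair in the Impaired or Diabetes range removes the error from that table.

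**Conclusion.** Wrong as written, and minor. For consecutive glucose pairs split between Impaired and Diabetes, with HbA1c available and below 5.7%, the footnote gives Normal against the table's own definition, and a better category than lower, concordant readings receive.

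The conclusion needs no distributional assumption, because it follows from the stated rules. It does rest on reading the footnote literally. The effect is confined to one descriptive shift table (worst and last versions) and its No change/Worsened/Improved summary, with no hypothesis test. The adverse-event search, the new-onset diabetes analysis and the separate glucose summaries are unaffected. The documents do not allow the number of participants to be estimated; three conditions must coincide, so it is probably small.

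**What to change.** Amend the three-asterisk footnote to say, in substance:

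> If two consecutive post-baseline fasting glucose values fall in different categories, the glucose category is the lower of the two, and the post-baseline category is the worse of that and the HbA1c category. If HbA1c is missing, the lower glucose category applies alone. If only one glucose value is available, HbA1c alone applies.

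The last two sentences keep existing rules and should not be dropped; without the second, the worse-of rule is undefined when HbA1c is missing. One limit remains: a single reading of 135 mg/dL with HbA1c 5.6% stays Normal, as now.

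The change costs one footnote and one line of derivation, plus a documented amendment. The current SAP already post-dates the primary analysis, after which most sponsor staff were to be unblinded (Protocol 6.4). The SAP history should therefore record the change as made after that analysis, with its reason. Rerun the Day 180 shift table so that it and the final table use the same rule.

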### Incidence of Post-baseline New-Onset of Diabetes

The number of participants who shift from no diabetes at baseline to post-baseline new onset of diabetes will be summarized.

The participant with no diabetes at baseline are those who had no medical history of diabetes in the targeted medical history CRF, had HbA1c  $<6.5\%$ , and had fasting glucose  $<126$  mg/dL prior to the study treatment (the baseline fasting glucose is defined as the average of fasting glucose values at Screening and Day 1. If one of the baseline fasting glucose values is missing, the assessment will be based on the available data).

A 4-component analysis will be utilized to detect the post-baseline new onset of diabetes. The 4 components are provided below.

1. Diabetic TEAEs identified by the SMQ search (see [Appendix 5.2](#)), or
2. Post-baseline fasting glucose  $\geq 126$  mg/dL on two consecutive occasions, or
3. Initiation of anti-diabetic medication at any time post-baseline, or
4. At least one post-baseline HbA1c  $\geq 6.5\%$ .

The number of participants who have any of the 4 components will be summarized (post-baseline new-onset of diabetes) by treatment group.

This analysis will be performed separately for participants who had normal and impaired glucose control categories at baseline.

The time to new-onset diabetes will also be summarized by treatment group. The number and percentage of participants meeting the 4 week interval category (<4 weeks, 4 to <8 weeks, 8 to <12 weeks, 12 to <16 weeks,  $\geq 16$  weeks) will also be summarized. Only participants without diabetes at baseline will be included in the analysis. The time (weeks) to new-onset diabetes will be calculated from the date of the first administration of study drug.

### **2.8.5 ECG and cardiac imaging data**

All ECG data will be summarized by visit and treatment group. A listing will be provided.

### **2.8.6 Vital signs**

Change from baseline in vital signs will be summarized descriptively at each scheduled time point by treatment group. For SBP and DBP, average of 3 readings will be used for analysis while all 3 readings in addition to the average will be provided in listing. Abnormalities will be flagged. The number and percentage of participants meeting clinical notable vital signs as defined below at any time (considering all data collected after first dose of double-blind treatment from scheduled, unscheduled, and premature discontinuation visit) will also be summarized.

**Table 2.8 Clinically notable vital signs**

Vital sign	Notable abnormalities (at any visit)	
Pulse (beats/min)	either $\geq 120$ & increase $\geq 25^*$ or $> 130$ either $\leq 50$ + decrease $\geq 30^*$ or $< 40$	
BP (mmHg)	systolic	either $\geq 180$ & increase $\geq 30^*$ or $> 200$ either $\leq 90$ & decrease $\geq 30^*$ or $< 75$
	diastolic	either $\geq 105$ & increase $\geq 20^*$ or $> 115$ either $\leq 50$ & decrease $\geq 20^*$ or $< 40$

\*Refers to post-BL value as compared to BL value

## 2.10 Immunogenicity

ADA evaluations, including treatment-emergent ADA findings and titers, will be summarized by visit and treatment group and listed. Additional analyses may be performed to describe the relationship between ADA and other study.

## 2.12 Interim analysis

There is no interim analysis planned.

### 3 Sample size calculation

Approximately 308 participants will be randomized by the IRT system: 100 participants for inclisiran sodium dose groups 200 mg and 300 mg; plus 54 participants in the placebo group and inclisiran sodium dose group 100 mg. Randomization will be stratified by current use of statins or other lipid-modifying therapies, LDL-C category at screening, [REDACTED].

The sample size assumption was based on the observed results from a previously completed Phase II Dose Finding Study (ORION-1). The difference in mean percentage change from baseline between the active dose groups and the placebo group for LDL-C at Day 180 is expected to be >30% with a standard deviation of approximately 20%.

The sample size of 308 will provide more than 90% power to detect a 30% reduction of LDL-C levels in at least one inclisiran sodium dose group compared to the placebo. Dunnett's test is used in order to control the family-wise type I error rate at a significance level of alpha=0.025 (one-sided test). [REDACTED].

### 4 Change to protocol specified analyses

The following change to protocol specified analyses was made:

- Proportion of participants in each group who attain lipid control target pre-specified by JAS 2022 was added because JAS 2017 was updated in July, 2022.

### 5 Appendix

#### 5.1 Imputation rules

##### 5.1.1 AE date imputation

The following table explains the notation used in the logic matrix. Please note that **missing start dates** will not be imputed.

	Day	Month	Year
Partial Adverse Event Start Date	Not used	MON	YYYY
Treatment Start Date	Not used	TRTM	TRTY

The following matrix explains the logic behind the imputation.

	MON MISSING	MON < TRTM	MON = TRTM	MON > TRTM
YYYY MISSING	(1) No convention	(1) No convention	(1) No convention	(1) No convention

YYYY < TRTY	( 2.a ) Before Treatment Start	( 2.b ) Before Treatment Start	( 2.b ) Before Treatment Start	( 2.b ) Before Treatment Start
YYYY = TRTY	( 4.a ) Uncertain	( 4.b ) Before Treatment Start	( 4.c ) Uncertain	( 4.c ) After Treatment Start
YYYY > TRTY	( 3.a ) After Treatment Start	( 3.b ) After Treatment Start	( 3.b ) After Treatment Start	( 3.b ) After Treatment Start

Before imputing AE start date, find the AE start reference date.

1. If the (imputed) AE end date is complete and the (imputed) AE end date < treatment start date then AE start reference date = min(informed consent date, earliest visit date).
2. Else AE start reference date = treatment start date

Impute AE start date -

1. If the AE start date year value is missing, the date uncertainty is too high to impute a rational date. Therefore, if the AE year value is missing, the imputed AE start date is set to NULL.
2. If the AE start date year value is less than the treatment start date year value, the AE started before treatment. Therefore:
  - a. If AE month is missing, the imputed AE start date is set to the mid-year point (01JulYYYY).
  - b. Else if AE month is not missing, the imputed AE start date is set to the mid-month point (15MONYYYY).
3. If the AE start date year value is greater than the treatment start date year value, the AE started after treatment. Therefore:
  - a. If the AE month is missing, the imputed AE start date is set to the year start point (01JanYYYY).
  - b. Else if the AE month is not missing, the imputed AE start date is set to the later of (month start point (01MONYYYY), AE start reference date + 1 day).
4. If the AE start date year value is equal to the treatment start date year value:
  - a. And the AE month is missing the imputed AE start date is set to the AE reference start date + 1 day.
  - b. Else if the AE month is less than the treatment start month, the imputed AE start date is set to the mid-month point (15MONYYYY).
  - c. Else if the AE month is equal to the treatment start date month or greater than the treatment start date month, the imputed AE start date is set to the later of (month start point (01MONYYYY), AE start reference date + 1 day).

If complete (imputed) AE end date is available and the imputed AE start date is greater than the (imputed) AE end date, then imputed AE start date should be set to the (imputed) AE end date.

- If the AE end date month is missing, the imputed end date should be set to the earliest of the (follow up period date, 31DECYYYY, date of death).
- If the AE end date day is missing, the imputed end date should be set to the earliest of the (follow up period date, last day of the month, date of death).
- If AE year is missing or AE is ongoing, the end date will not be imputed.

### 5.1.2 Concomitant medication date imputation

The following table explains the notation used in the logic matrix. Please note that **missing start dates** will not be imputed.

	Day	Month	Year
Partial CMD Start Date	Not used	MON	YYYY
Treatment Start Date	Not used	TRTM	TRTY

The following matrix explains the logic behind the imputation.

	MON MISSING	MON < TRTM	MON = TRTM	MON > TRTM
YYYY MISSING	( 1 ) Uncertain	( 1 ) Uncertain	( 1 ) Uncertain	( 1 ) Uncertain
YYYY < TRTY	( 2.a ) Before Treatment Start	( 2.b ) Before Treatment Start	( 2.b ) Before Treatment Start	( 2.b ) Before Treatment Start
YYYY = TRTY	( 4.a ) Uncertain	( 4.b ) Before Treatment Start	( 4.a ) Uncertain	( 4.c ) After Treatment Start
YYYY > TRTY	( 3.a ) After Treatment Start	( 3.b ) After Treatment Start	( 3.b ) After Treatment Start	( 3.b ) After Treatment Start

1. If the CM start date year value is missing, the imputed CM start date is set to one day prior to treatment start date.
2. If the CM start date year value is less than the treatment start date year value, the CM started before treatment. Therefore:
  - a) If the CM month is missing, the imputed CM start date is set to the mid-year point (01JulYYYY).
  - b) Else if the CM month is not missing, the imputed CM start date is set to the mid-month point (15MONYYYY).
3. If the CM start date year value is greater than the treatment start date year value, the CM started after treatment. Therefore:
  - a) If the CM month is missing, the imputed CM start date is set to the year start point (01JanYYYY).

- b) Else if the CM month is not missing, the imputed CM start date is set to the month start point (01MONYYYY).
- 4. If the CM start date year value is equal to the treatment start date year value:
  - a) And the CM month is missing or the CM month is equal to the treatment start date month, then the imputed CM start date is set to one day prior treatment start date.
  - b) Else if the CM month is less than the treatment start date month, the imputed CM start date is set to the mid-month point (15MONYYYY).
  - c) Else if the CM month is greater than the treatment start date month, the imputed CM start date is set to the month start point (01MONYYYY).

If complete (imputed) CM end date is available and the imputed CM start date is greater than the (imputed) CM end date, then imputed CM start date should be set to the (imputed) CM end date.

- If CM end day is missing and CM month/year are non-missing then impute CM day as the minimum of disposition date and the last day of the month.
- If CM end day/month are missing and CM year is non-missing then impute CM day as the minimum of disposition date and the end of the year (31DECYYYY).
- Only include if ongoing records will not be imputed.
- If imputed CM end date is less than the CM start date, use the CM start date as the imputed CM end date.

Above rules apply to concomitant surgical and medical procedures as well.

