**Table 2-4 High/Moderate/Low intensity statin therapy**

	High intensity	Moderate intensity	Low intensity
Statin name and dose/day	Atorvastatin 40 mg Rosuvastatin 20 mg	Atorvastatin $\geq$ 10 and < 40 mg Rosuvastatin $\geq$ 5 and < 20 mg Simvastatin 20 mg Pitavastatin 1-4 mg	Atorvastatin < 10 mg Rosuvastatin < 5 mg Simvastatin $\leq$ 10 mg Pravastatin $\leq$ 20 mg Fluvastatin $\leq$ 60 mg

Respecting reference 2018 AHA/ACA classification but taking into account the eventuality that some study subjects may be on doses falling between the consensus categories.

New or changed lipid-modifying therapy after baseline using the same categories as above will be summarized by treatment group.

Prior medications and other concomitant medications will be summarized by treatment group according to the Anatomical Therapeutic Chemical (ATC) classification system. Significant non-drug therapies (surgical and medical procedures) will be summarized by treatment group, according to the SOC and PT in the MedDRA dictionary.

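### Medication start dates that the SAP labels uncertain are all set to the day before first dose, so a new antidiabetic or lipid-modifying drug dated that way drops out of two planned summaries

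*SAP*

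**What the plan says.** SAP 5.1.2 crosses the start year with the start month, each compared with first dose. The cells it labels *Uncertain* are those with the year missing, and those with the treatment year and the month either missing or equal to the treatment month.

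- Rule 1, year missing: "If the CM start date year value is missing, the imputed CM start date is set to one day prior to treatment start date".
- Rule 4a, treatment year with month missing or equal: "then the imputed CM start date is set to one day prior treatment start date".
- Rule 4c, treatment year with a later month: "the CM month is greater than the treatment start date month, the imputed CM start date is set to the month start point".
- Rule 3, later year: "If the CM start date year value is greater than the treatment start date year value, the CM started after treatment".

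The section opens with a sentence that points the other way from rule 1: "Please note that missing start dates will not be imputed".

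Two planned outputs depend on whether a drug was started after baseline. Component 3 of the new-onset diabetes definition in SAP 2.8.4 is "Initiation of anti-diabetic medication at any time post-baseline". SAP 2.4.2, after Table 2-4, states: "New or changed lipid-modifying therapy after baseline using the same categories as above will be summarized by treatment group".

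For adverse events, SAP 5.1.1 rule 4a reads: "And the AE month is missing the imputed AE start date is set to the AE reference start date + 1 day". Its rule 4c gives the same result for an event dated only to the treatment month.

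**The concern.** Section 5.1.2 is the SAP's only rule for medication dates, and it makes no exception for drugs whose start is itself an outcome. A drug that was truly new but falls in an uncertain cell is treated as started before first dose, so neither of the two summaries counts it.

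For diabetes the loss runs in one direction. SAP 2.8.4 defines no diabetes at baseline by medical history, HbA1c and fasting glucose, not by medication. A participant whose new antidiabetic drug is backdated therefore stays in the group at risk and loses the component 3 event. If another component catches the case later, the time to onset is lengthened.

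For lipid drugs, the summary exists to show how far background therapy changed after baseline. An addition dated to the day before first dose disappears from it and looks like a screening-phase addition, which Protocol Table 6-2 handles differently from one made during treatment.

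**Working it through.** The plan gives no figure for this rule, so there is none to reproduce. The check works through the rule itself.

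**1. Cells affected.** Four year states (missing, earlier, same, later) by four month states (missing, earlier, same, later) give 16 cells. Year missing contributes 4 cells and same year with month missing or equal contributes 2. So 4 + 2 = 6 of 16 cells go to the day before first dose. The other 10 do not.

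**2. Comparison with the adverse-event rule**, using an illustrative first dose on 10 June 2021:

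| Recorded start | Medication (5.1.2) | Adverse event (5.1.1) |
|---|---|---|
| June 2021 | 9 June 2021 (before) | 11 June 2021 (after) |
| 2021 | 9 June 2021 (before) | 11 June 2021 (after) |
| September 2021 | 1 September 2021 (after) | 1 September 2021 (after) |
| 2022 | 1 January 2022 (after) | 1 January 2022 (after) |
| Year missing | 9 June 2021 under rule 1; not imputed under the opening sentence | Set to NULL |

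The adverse-event column takes first dose as the reference date. This holds unless the event has a complete end date before treatment.

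**3. Share of truly new drugs moved before first dose.** Assumptions: true starts uniform over Days 2 to 360 (359 days), and first-dose dates uniform over a 365-day year.

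- *Only the day missing.* A start is moved if it falls later in the month of first dose. A month of L days contributes L(L−1)/2 such first-dose and start-day pairs: 7 × 465 + 4 × 435 + 378 = 5,373. Mean share = 5,373 / (365 × 359) = 4.1%. Range: 0 (first dose on the last day of a month) to 30/359 = 8.4%.
- *Day and month missing.* A start is moved if it falls later in the calendar year of first dose. The days left run from 0 to 364, capped at 359: 359 × 360/2 + 5 × 359 = 66,415. Mean share = 66,415 / (365 × 359) = 50.7%. Range: 0 to 100%, depending on the date of first dose.
- *Year missing.* 100% if rule 1 is applied.

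**4. Lipid drugs and eligibility.** Protocol inclusion criterion 9 requires lipid therapy stable for at least 30 days before screening, and screening is at the latest on Day −1. Qualifying therapy therefore started at least 31 days before Day 1. No month has more than 31 days, so that start always lies in an earlier calendar month. In an eligible participant, a lipid drug dated only to the treatment month cannot be qualifying background therapy, yet rule 4a dates it to Day −1. This argument does not extend to a record with the month missing, since qualifying therapy could have started earlier in the same year.

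**The case against.** The strongest reply is that some direction must be chosen for records that cannot be dated, that the choice is largely convention, and that little follows from it here. Much of that stands.

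- A reader might infer that all partial dates are backdated. They are not: a known later month or year goes after first dose.
- A reader might infer that the special-interest table for diabetes is undercounted. SAP 2.8.1.1 builds that table from adverse-event search criteria, and event dates follow 5.1.1. The medication rule does not reach it.
- A reader might infer that the primary result is affected. The estimand uses a treatment-policy strategy for treatment discontinuation and for dose changes in allowed medication, and no LDL-C value is removed because of a medication date. Day −1 also normally stays inside the prohibited window of Protocol Table 6-2, and prohibited medication is tabulated as a protocol deviation.
- A diabetes case counts if any of four components is met, so an event term, glucose or HbA1c may still find it. Protocol 8.4.4.2 also has new medications checked for hyperglycemia-related events.
- The SAP does not say outright that imputed dates feed the two summaries. Lipid therapy is recorded at screening and Day 1, so a programmer could recognise a new agent from that record. The drug also remains a concomitant medication.

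What does not stand is that the convention is neutral. For lipid drugs dated to the treatment month, eligibility makes Day −1 the less plausible date. For participants without diabetes by history and laboratory values, it is the anti-conservative one. The other components are an incomplete safeguard: after baseline, HbA1c is tested only at Days 90, 180 and 360 (Protocol Table 8-3), and a glucose-lowering drug may itself hold laboratory values below threshold.

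**Conclusion.** The point holds for the uncertain cells only. In those cells a truly new antidiabetic or lipid-modifying drug is dated before first dose and leaves component 3 and the new or changed lipid therapy summary. The SAP resolves the same-year cells in the opposite direction for adverse events. For a missing year the two rules differ in another way, since the adverse-event rule leaves the date empty. For a wholly missing medication date, 5.1.2 contradicts itself.

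The size is conditional: about 4% of truly new starts when only the day is missing, about 51% when day and month are missing, and all of them when the year is missing and rule 1 applies. These shares rest on the uniformity assumptions above. The documents do not give the frequency of partial dates, so no number of participants can be stated.

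A reader might reckon that if 1 to 3 of 10 new antidiabetic drugs had partial dates, 10 to 30% of component 3 would be lost. That would treat every partial date as uncertain. If only the day were missing, the expected loss would be 1 × 0.04 to 3 × 0.04, or about 0.04 to 0.12 records. The effect is on two descriptive summaries and on time to new-onset diabetes, not on the primary analysis.

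**What to change.** For antidiabetic and lipid-modifying drugs not recorded as in use at screening or Day 1, set same-year uncertain start dates to first dose plus one day for these two summaries. This is the SAP's own adverse-event convention, and the end-date cap already in 5.1.2 applies. Alternatively, report both summaries under both conventions. That is the safer choice if the change comes after the Day 180 unblinding of sponsor members. Keep the current rule for all other drugs.

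Reconcile the sentence that missing start dates are not imputed with rule 1, and state how a missing year is handled for these two classes, where the adverse-event rule offers no date.

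The cost is one SAP paragraph and one programming branch. A few pre-existing drugs may be counted as new, which is the conservative direction for safety. Diabetes cases dated only by this imputation would also fall in the under-4-weeks category of time to onset, so they should be footnoted there.
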